3.1.8 Slit-Lamp Biomicroscopy

The biomicroscopy exam will be performed at Visit 2 and Visit 5. It should be performed with the Slit-Lamp using a beam of width and intensity to provide optimal evaluation of anterior segment. Normal or abnormal assessments will be made for each of the 11 individual criteria. This assessment will be measured and summarized in each eye separately.

This procedure will be performed in the same manner for all subjects observed at the Investigator's site.

3.2 Adverse and Serious Adverse Events

3.2.1 Adverse Event (AE)

Any untoward medical occurrence in a subject administered a pharmaceutical product and which does not necessarily have a causal relationship with this treatment is an adverse event (AE). An AE can therefore be any unfavorable and unintended sign (including an abnormal laboratory finding), symptom, or disease temporally associated with the use of a medicinal (investigational) product, whether or not related to the medicinal (investigational) product.

3.2.2 Adverse Drug Reaction (ADR)

In the pre-approval clinical experience with a new medical product or its new usages, particularly as the therapeutic dose(s) may not be established, all unintended responses to a medicinal product related to any dose should be considered adverse drug reactions (ADRs). The phrase "responses to a medicinal product" means that a causal relationship between a medicinal product and an AE is at least a reasonable possibility, i.e., the relationship cannot be ruled out.

3.2.3 Serious Adverse Event

An SAE is an untoward medical occurrence that at any dose meets one or more of the following criteria:

- Results in death (Note: death is an outcome, not an event)
- Is life-threatening (Note: the term "life-threatening" refers to an event in which the subject was at immediate risk of death at the time of the event; it does not refer to an event which could hypothetically have caused a death had it been more severe)
- Requires in-patient hospitalization or prolongation of existing hospitalization
- Results in persistent or significant disability/incapacity

- Results in a congenital anomaly/birth defect
- Is a medically important event or reaction

3.2.4 Suspected Unexpected Serious Adverse Reaction (SUSAR)

Any ADR that is both serious and unexpected (per the Investigator's Brochure [IB]) that, based on the opinion of the Investigator or Aurinia, is felt to have a reasonable suspected causal relationship to a medicinal product is a suspected unexpected serious adverse reaction (SUSAR).

3.2.5 Treatment-Emergent Adverse Event (TEAE)

A treatment emergent adverse event (TEAE) is defined as any AE that has an onset on or after the first dose of IP/study drug and on or before the last dose of IP/study drug plus 3 days.

3.2.6 Intensity/Severity Categorization

The term "severe" is often used to describe the intensity (severity) of a specific event (as in mild, moderate, or severe myocardial infarction); however, the event itself may be of relatively minor medical significance (such as severe headache). This is not the same as "serious," which is based on subject/event outcome or action criteria usually associated with events that pose a threat to a subject's life or functioning. Seriousness (not severity) serves as a guide for defining regulatory reporting obligations.

In general, the intensity of a particular AE to be recorded is the worst intensity experienced by the subject during the course of the event. The medical assessment of intensity will be determined by using the following definitions:

Mild: The AE is easily tolerated and does not interfere with usual activity.

Moderate: The AE interferes with daily activity, but the subject is still able to function.

Severe: The AE is incapacitating, and the subject is unable to work or complete usual activity.

3.2.7 Causal Relationship Categorization

An Investigator who is qualified in medicine must make the determination of relationship to the study treatment for each AE and SAE. The Investigator must decide whether, in his or her medical judgment, there is a reasonable possibility that the event may have been caused by the study treatment. If there is no valid reason for suggesting a relationship, then the AE/SAE must be classified as not related. Otherwise, if there is any valid reason, even if undetermined or untested, for suspecting a cause-and-effect relationship between the study treatment and the occurrence of the AE/SAE, then the AE/SAE will be considered related. For SAEs, the Investigator must provide a brief comment explaining the rationale of his/her assessment of causal relationship on the SAE reporting form.

The following additional guidance may be helpful:

Term	Relationship	Definition
Related	Yes	The temporal relationship of the clinical event to study drug administration indicates a causal relationship, and other drugs, therapeutic interventions or underlying conditions do not provide a sufficient explanation for the observed event.
Not related	No	The temporal relationship of the clinical event to study drug administration does not indicate a causal relationship, or other drugs, therapeutic interventions or underlying conditions provide a sufficient explanation for the observed event.

If the causal relationship between an AE/SAE and the study treatment is determined to be “related”, the event will be considered to be related to study treatment for the purposes of expedited regulatory reporting. In circumstances where the Investigator has not yet provided his/her assessment about the relationship, the event will be considered as “related” and qualify for expedited regulatory reporting.

3.2.8 Outcome Categorization

Outcome may be classified as recovered without sequelae; recovered with sequelae; improved; worsened; ongoing; ongoing at end of study; fatal; or unknown. If the outcome is reported as recovered with sequelae for an SAE, the Investigator should specify the kind of sequelae on the SAE reporting form. SAEs that are ongoing at the time of death will have an outcome of “unknown” recorded. SAEs resulting in a fatal outcome will have an outcome of “fatal” recorded.

3.2.9 Symptoms of the Disease Under Study

Symptoms and fluctuations in laboratory parameters related to the disease under study will not be classed as AEs as long as they are within the normal day-to-day fluctuation of the disease. An explanation of these circumstances must be written in the source documents.

Worsening of the symptoms or laboratory parameters, however, will be recorded as an AE and clearly marked as worsening or by the subject’s worst observed intensity. The Investigator will be required to assess the relationship to disease under study for each AE as related or not related. An AE will not be able to be assessed as related to both disease under study and related to study treatment.

4.0 SAMPLE SIZE AND POWER CONSIDERATIONS

The study will include approximately 90 male or female subjects.

The primary analysis will use a t-test and will assess the difference in change from baseline in Drop Discomfort VAS scores (range 0 to 100 mm) 1-minute post-Dose 1 instillation between the two treatment groups.

A sample size of 38 subjects per group (76 in total) will provide 90% power assuming:

- A mean change from baseline Drop Discomfort VAS score of +30 mm for subjects randomized to Restasis®
- A mean change from baseline Drop Discomfort VAS score of +15 mm for those randomized to VOS
- These assumed mean changes lead to a 15 mm lower change from baseline in VAS scores for VOS compared to Restasis®
- A common standard deviation of 20 mm
- A 2-sided alpha of 5%

Under the same assumptions, the study will have at least 80% power if the common standard deviation for the discomfort score were to be 23 mm.

The study also provides 80% power should the treatment difference in discomfort scores be 13 (common standard deviation=20 mm).

To allow for 15% dropouts, approximately 90 subjects will be randomized.

It is interesting to note that a power of 80% is achieved by this sample size when the treatment difference (VOS- Restasis®) is 12 mm in favor of VOS and alpha is 10%.

5.0 ANALYSIS POPULATIONS

Three populations will be used for analysis.

5.1 Efficacy Analysis Populations

5.1.1 Intent-to-Treat Set

The tolerability and efficacy analysis will be based on the intent-to-treat (ITT) principles and will consist of all randomized subjects who receive at least 1 dose of study treatment. The subjects in this group will be analyzed based on the planned treatment.

5.1.2 Per Protocol Set

The per-protocol set will be a subset of subjects in the ITT population who do not have any major protocol violations (to be defined prior to unmasking). The subjects in this group will be analyzed based on the treatment they received.

5.1.3 Safety Analysis Set

The safety analysis set will consist of all randomized subjects who receive at least 1 dose of study treatment. The subjects in this group will be analyzed based on the treatment they received.

6.0 HANDLING OF MISSING DATA

No specific methods for handling of missing data are proposed. Observed cases will be analyzed.

6.1 Conventions for Missing and Partial Dates

All rules explained below for partial/missing dates will be followed unless contradicted by any other data recorded on the electronic Case Report Form (eCRF).

All dates presented in the individual subject listings will be as recorded on the eCRF (i.e., not completed as per the below rules).

6.2 Missing/Partial Start/Stop Date of Adverse Events and Concomitant Medications

Missing and partial start and stop date will be imputed for analysis purposes as follows

Partial or missing stop date will be imputed as follows:

- If the stop date is completely missing and the event has resolved or the subject has stopped taking the concomitant medication, the stop date will be imputed as the date of the subject's last clinic visit in the study.
- If only the year is known, the stop date will be imputed as "31-Dec" of that year or as the date of the subject's last clinic visit in the study if in the same year.
- If the month and year are known, the stop date will be imputed as the last day of that month unless the stop date corresponds to the same month as the subject's last clinic visit in which case the date of subject's last clinic visit in the study will be used instead.

Missing start date will be imputed as follows:

- If the stop date occurs on or after the start of study drug or the event/concomitant medication is ongoing, the start date will be imputed as the date of the first dose of study drug.
- If the stop date occurs before the start of study drug, the start date of the event/concomitant medication will be imputed as the subject's screening date or the stop date of the event/concomitant medication whichever the earlier.

Partial start date (year present, but month and day missing)

- If the stop date occurs on or after the start of study drug or the event/concomitant medication is ongoing, and the year is the same as the year of first dosing the start date will be imputed as "01-Jan" of the same year or the date of the first dose of study drug whichever is latest. If the year is different from the year of first dosing "01-Jan" will be used.

- If the stop date occurs before the start of study drug, the start date of the event/concomitant medication will be imputed as the “01-Jan” of the same year.

Partial start date (month and year present, but day missing)

- If the stop date occurs on or after the start of study drug or the event/concomitant medication is ongoing, the start date will be imputed as the first day of the same month and year unless this partial start date is in same month as the first dose of study drug in which case the date of first dose of study drug will be used.
- If the stop date occurs before the start of study drug, the start date will be imputed as the first day of the month and year of the partial stop date.

6.3 Missing Last Dates of Study Drug Dosing

If the date of last dose of study drug is completely missing, then the date of last dose of study drug will be taken for analysis purposes as the date when the subject would have run out of study drug assuming full compliance from the date the study drug was last dispensed or the date of subject’s last clinic visit in the study or early withdrawal or death whichever is earlier.

If only the month and year of the last dose was recorded, then the date of last dosing will be taken for analysis purposes as the date the subject would have run out of study drug assuming full compliance from the date the study drug was last dispensed, the last day of the month of the recorded last dose or the date of subject’s last clinic visit in the study or early withdrawal or death whichever the earlier.

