8.2.2.2 VISIT 3 (Treatment Day 7 \pm 2)

The site staff will perform/assess the following procedures:

- SANDE
- Individual Symptom Severity Assessments (VAS)
- AE assessment
- Concomitant medication review
- **Unmasked dedicated dosing coordinator** will collect returned carton containing used and unused IP ampules
- **Unmasked dedicated dosing coordinator** will collect Dosing Diary, Drop Comfort VAS and dispense new Dosing Diary and Drop Comfort VAS

- **Unmasked site staff** will query the subject regarding compliance with dosing and the protocol. If the subject has not been compliant with the dosing regimen, record this in the source document and eCRF and discuss proper compliance with the subject
- BCVA assessment
- IP Administration:
 - The **unmasked dedicated dosing coordinator** will administer the AM dose of IP in the clinic
- Drop Discomfort VAS:
 - The **masked site staff** will administer the Drop Discomfort VAS at 1-minute and 5-minutes post-dose
- Assess for occurrence of any AEs following instillation
- **Unmasked dedicated dosing coordinator** will dispense IP to the subject
- FCS
- Evening contact scheduling: **Masked site staff** will schedule and contact the subject in the evening of the clinic visit to prompt administration of the next dose and completion the Drop Discomfort VAS
- Remind subject to withhold AM dose of IP on morning of next clinic visit and to return all used and unused IP

Schedule the subject to return in 1 week for Visit 4 on Day 14 \pm 2 days.

PM Contact with Patient:

- **Masked site staff** will call subject to prompt IP administration and will remain on call to facilitate completion of the Drop Discomfort VAS at 1-minute and 5-minutes post-dose

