7.4 Treatment Compliance and Exposure

The duration of drug exposure and % compliance will be summarized by treatment group.

Duration of drug exposure will be calculated for each subject as the last date of dosing minus the first date of dosing + 1. The number and percentage of subjects by treatment group will be summarized according to the following duration-of-exposure categories: '< 1 wk', '1 to < 3 wks', '3 to < 5 wks' and '≥ 5 wks.'

A subject data listing will be provided.

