8.0 SAFETY EVALUATIONS

8.1 Adverse Events

For screen failure subjects, any AEs and SAEs occurring during the screening period (after informed consent) will be recorded in the subject's source documentation only and will not be collected on the eCRF.

For enrolled subjects, all AEs and SAEs will be recorded in the AE section of the subject's eCRF and source documentation.

A treatment emergent adverse event (TEAE) is defined as any AE that has an onset on or after the first dose of IP/study drug and on or before the last dose of IP/study drug plus 3 days. Only treatment-emergent events will be summarized. All events in the clinical database regardless of when they occurred will be provided in data listings i.e., for enrolled subjects, data listings will have screening AEs/SAEs and TEAEs/serious TEAEs. Adverse events will be presented by Medical Dictionary of Regulatory Activities (MedDRA) primary system organ class (SOC) and preferred term (PT).

An overall summary will be presented which gives the number and percentage of subjects within each treatment group (n (%)), and the number of events (E) that experienced:

- Any TEAE
- Any Treatment-Related TEAE
- Any Disease-Related TEAE
- Any Serious TEAE
- Any Serious Treatment-Related TEAE
- Any Serious Disease-Related TEAE.
- Any TEAE Leading to Study Drug Discontinuation
- Any Treatment-Related TEAE Leading to Study Drug Discontinuation
- Any Disease-Related TEAE Leading to Study Drug Discontinuation
- Any TEAE with Outcome of Death
- Any Treatment-Related TEAE with Outcome of Death
- Any Disease-Related TEAE with Outcome of Death

In summary tables, ocular AEs recorded once for each eye separately but in the same timeframe will be summarized once at the greater intensity and relationship to study drug. The number and percentage of subjects experiencing one or more events within a MedDRA SOC and PT class without regard to intensity, relationship, or seriousness will be tabulated by treatment group. Additional tables for TEAEs and Serious TEAEs will display events by SOC, PT, and maximum intensity.

The following Adverse Event listings will be provided:

- Listing of TEAEs by treatment group ordered by subject, SOC, PT, and date (study day)
- Listing of serious TEAEs by treatment group ordered by subject, SOC, PT, and onset date (study day)
- Listing of TEAEs leading to study drug interruption or discontinuation
- Listing of TEAEs resulting in death
- Listing of all AEs not classified as Treatment Emergent

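### For a subject not seen again after a dispensing visit, the missing-last-dose rule returns the dispensing day, which cuts the TEAE window and the recorded exposure short

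*SAP*

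**What the plan says.** SAP 6.3 has two rules. For a completely missing last-dose date, the candidates are the day supply would have run out, "assuming full compliance from the date the study drug was last dispensed", and the subject's "last clinic visit in the study or early withdrawal or death whichever is earlier". Where only month and year are known, the candidates are the same plus the last day of the recorded month, and again the earliest is used.

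The imputed date has two uses:

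- **TEAE window.** SAP 3.2.5 requires onset on or after the first dose and "on or before the last dose of IP/study drug plus 3 days". SAP 8.1 repeats this and adds: "Only treatment-emergent events will be summarized". Other events appear only under "Listing of all AEs not classified as Treatment Emergent".
- **Exposure.** SAP 7.4: "Duration of drug exposure will be calculated for each subject as the last date of dosing minus the first date of dosing + 1".

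The Schedule of Events shows dispensing at Visits 2, 3 and 4. At Visit 3, for example, Protocol 8.2.2.2 says that the unmasked dosing coordinator "will dispense IP to the subject". Diaries and used ampules come back at the next clinic visit.

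SAP 6.1 adds a general override: the date rules give way where other data on the eCRF contradict them.

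**The concern.** A last-dose date is likely to be missing when a subject takes drug home and does not come back with the diary. For such a subject the last clinic visit is the dispensing visit. The rule then assumes no home dosing after that day, although the run-out clause seems to have been written for exactly this case.

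If the imputed last dose is too early, an event that began during home dosing can be classed as not treatment-emergent. It would then be missing from the TEAE summaries, and also from the listing of events leading to interruption or discontinuation, because SAP 8.1 restricts that listing to TEAEs. Safety is a secondary objective. With about 45 subjects per arm, one subject is 1/45, or about 2 percentage points, in any of these tables.

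The rule also runs against the SAP's other conventions, which resolve gaps towards counting events. A completely missing start date goes to first dose if the event is ongoing or stopped on or after first dose (6.2). Missing relationship counts as related, and missing severity as severe (6.5).

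**Working it through.** No figure stated in the plan depends on this rule, so there is none to reproduce. The check is date arithmetic.

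**Inputs**

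- Nominal visit days (Schedule of Events): Visit 2 = 1, Visit 3 = 7, Visit 4 = 14, Visit 5 = 28, with ±2 days for Visits 3 to 5.
- Imputed last dose (SAP 6.3) = min(run-out, last clinic visit, early withdrawal, death).
- Window close (SAP 3.2.5) = last dose + 3.
- Exposure (SAP 7.4) = last dose − first dose + 1. With first dose on Day 1, this equals the day number of the last dose.
- Run-out day: not given, because the number of ampules per dispensing is not stated. Assumed to be the next nominal visit day. The range runs from the day before that visit to the end of its window.

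**Step 1. Which candidate is earliest?** Run-out is counted from the last dispensing, so it cannot fall before that visit. Withdrawal and death cannot fall before a visit the subject attended. If the last attended visit is the dispensing visit, the minimum is always that visit.

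**Step 2. Resulting dates** (ranges in brackets)

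| Last visit attended | Imputed last dose | Window closes under SAP | Window closes from run-out | Days cut | Exposure: SAP vs run-out |
|---|---|---|---|---|---|
| Visit 2, Day 1 | min(7, 1) = 1 | 1 + 3 = 4 | 7 + 3 = 10 (9–12) | 6 (5–8) | 1 vs 7 days (6–9) |
| Visit 3, Day 7 | min(14, 7) = 7 | 7 + 3 = 10 | 14 + 3 = 17 (16–19) | 7 (6–9) | 7 vs 14 days (13–16) |
| Visit 4, Day 14 | min(28, 14) = 14 | 14 + 3 = 17 | 28 + 3 = 31 (30–33) | 14 (13–16) | 14 vs 28 days (27–30) |

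After Visit 4, 14 days falls in the SAP 7.4 category of 1 to under 3 weeks. Any value from 27 to 30 days falls in 3 to under 5 weeks.

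**Step 3. The month-and-year rule.** Illustration with assumed dates: Visit 4 on 30 July, last dose recorded as August, no later visit. The candidates include 30 July (last clinic visit) and 31 August (end of recorded month). The minimum is 30 July, which contradicts the month on record.

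**Step 4. When is an event actually lost from the summaries?** All of these must hold:

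1. The last-dose date is missing or partial.
2. There is no early-termination or unscheduled visit after the last dispensing.
3. The event still reaches the eCRF. This is possible: Protocol 9.3.1 foresees telephone contact, and Protocol 8.2.2.4 has a call on the evening before Visit 5.
4. Onset is known and more than 3 days after the dispensing visit.
5. No other eCRF data contradict the imputed date.

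**Step 5. How many subjects?** The sample-size allowance is 15% of 90 = 13.5 dropouts. That is a planning figure for all dropouts. Subjects who meet every condition in Step 4 will be fewer, and the documents give no basis for a number.

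**The case against.** **The SAP 6.1 override.** A reader might infer that an event which makes a subject stop at home would drop out of the count of TEAEs leading to discontinuation. The documents do not support that as a firm result. Protocol 5.6 requires the specific event behind a stop to be in the eCRF, and Protocol 9.3.1 requires onset date and action taken. An event starting on Day 5 and recorded as the reason for stopping is hard to square with a last dose on Day 1, so SAP 6.1 arguably removes the imputed date. What stands is that SAP 6.1 names no replacement date and does not say that such an entry counts as a contradiction. The outcome is left to whoever programs it.

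**Another reading of SAP 6.3.** Last visit, withdrawal and death could be meant as one end-of-participation date, compared with run-out. This has some force, because the withdrawal and death terms do little in a four-way minimum. It would help a subject with a recorded withdrawal date. A subject lost to follow-up, with no such date, would still be placed at the last clinic visit.

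**Rarity.** The protocol asks for Visit 5 assessments from those who leave early, and a subject who is wholly out of touch reports no event to lose. An event with a completely missing start date that is ongoing or ended after first dose is set to first dose and stays a TEAE. All of this stands, and it limits the size of the problem.

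**Conclusion.** The rule gives the wrong date in a situation the plan foresees, since loss to follow-up is a listed reason for discontinuation in SAP 7.2. For a subject last seen at Visit 2, 3 or 4, the run-out clause has no effect. The TEAE window closes on Day 4, 10 or 17 instead of about Day 10, 17 or 31, and exposure is understated by up to about 6, 7 or 14 days. These figures rest on nominal visit days and on supply lasting to the next visit.

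The consequence is minor. The number affected is probably small, excluded events remain in the listing of non-treatment-emergent events, the exposure table is descriptive, and the primary endpoint (1 minute after the first dose at Visit 2) is untouched.

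A reader might infer that the less tolerable product would lose more events and so look better. The documents do not show this. SAP 7.2 lists many reasons for stopping besides tolerability, and nothing ties missing last-dose dates to one arm. Nor should the 13 to 14 planned dropouts be read as events lost.

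**What to change.** 1. **SAP 6.3, both rules.** For subjects with no clinic visit after the last dispensing, replace the last clinic visit with the date of last contact. The imputed date becomes the earliest of run-out, last contact or withdrawal, and death, and in the month-and-year rule also the end of the recorded month. Define contact to include any report from the subject by telephone. A reported event is then itself a contact on or after its onset.
2. **SAP 3.2.5 and 8.1.** State that an event with onset on or after first dose, recorded as leading to discontinuation of study drug, is a TEAE. This makes the SAP 6.1 override explicit for the case that matters most.
3. **SAP 7.4.** Footnote exposure based on an imputed last dose.

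The cost is a few SAP sentences and a small programming change before database lock. There are two limits. Exposure may be slightly overstated for a subject who stopped soon after dispensing but was in contact later. For a subject with no contact at all after the dispensing day, the imputed date is still that day. No reported event is lost there, but the exposure is a lower bound, which the footnote should say.
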